#### **D.2.e. Initial Assessment:** Trained interviewers will perform initial data collection.

- Contact information, including email address, best times to reach the patient, contact information for 2 additional individuals, and PCP.
- Type of diabetes, duration, complications, reason for hospital admission
- Age, gender, race and ethnicity, education level, marital status, work status, home ownership, insurance coverage, medical history, concomitant medications, weight, height, BMI, standard of care lab results
- Social support is an environmental factor that is associated with readmissions, determines behavior in SCT and influences self-efficacy. It will be measured using the Multidimensional Scale of Perceived Social Support (PSSS).
- Health literacy is a determinant of hospital readmissions and will be assessed using the Newest Vital Sign.
- Diabetes Empowerment Scale Short-Form (DES-SF) measures perceived self-efficacy and predicts adherence to a therapeutic plan. The DES-SF has been shown to have acceptable reliability ( $\alpha=0.84$ ).
- Comorbidity is key determinant of readmission; it is measured with the Charlson comorbidity index.
- It is anticipated that nearly all patients who are hospitalized with an HbA1c >8.5% will go home on insulin therapy. The complexity of the discharge regimen will be assessed as number of injections per day, total units per day, and number of glucose checks per day.

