**Table 8. Diabetes Order Set Summary**

Standard Elements		
Diabetes-specific elements	Detail	Prescriber Guidance
Diet	Choice of consistent (defaults to 45 or 60 gram/meal) or flexible carbohydrate	Selection criteria for flexible carb diet.
Follow-up and referrals	Choice of primary care or endocrinology (call for appointment for *** weeks, appointment has been made for ***) Diabetes education (general education or survival skills)	Only local patients should be referred to OSU.
Patient instructions	Call provider for hypoglycemia Call provider for hyperglycemia Bring glucose log to appointment Glucose targets Home diabetes management attachment	Identification of glucose targets
Insulin prescriptions	Each insulin is presented as a panel, linked to pen needle or syringe as appropriate Each insulin Rx defaults to 3 pen or 1 vial with 1 refill Insulins categorized by basal, prandial set meal dose with correction, or prandial flexible meal dose with correction	Number of units per pen or vial Syringe size Titration options for basal insulin Selection criteria for flexible meal dosing Correction dosing from pick list of low, standard, or high doses
Glucose Monitoring supplies	Panels categorized by frequency of monitoring Each panel contains glucometer, test strips, lancets, alcohol wipes Prescriptions default to dispense appropriate number of supplies with 1 refill	Guidance on monitoring frequency
Other DM supplies	Ketone strips Glucagon	Selection criteria provided for each

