#### H.1.a. Missing Data

All data analyses will be completed as intention to treat analyses (i.e., individuals analyzed by group according to original random assignment, without regard to adherence to the intervention).

Longitudinal outcomes (e.g., HbA1c) will be analyzed using mixed models utilizing all available measurements from individuals randomized. Missing binary outcomes (e.g., accurate and complete discharge orders, adherence) and missing covariate data will be imputed, using multiple imputation in SAS v9.3 PROC MI.

Table 9. Study Procedures and Visits

Visit number	0	1	2	3	4
Time of Visit	Screen/consent	2 week	6 week	12 week	24 week
Type of visit	In-person	Phone	Phone	In-person	In-person
Informed consent/contact team	x				
Randomization	x				
Load DOS into EMR and inform discharge team	x				
Provide study drug and glucose monitoring instructions	x				
Demographics/Socioeconomic status	x				
Diabetes history	x				
Hospitalization history	x				
PSS scale	x				
DES-SF	x			x	x
Newest Vital Sign	x				
Glucose/insulin diary	x				
Review DOS		x			
Ascertain health care utilization		x	x	x	x
Review glucose/insulin diary		x	x	x	x
Hypoglycemia/Hyperglycemia		x	x	x	x
Review insulin adherence, persistence		x	x	x	x
Nurse counsellor (DOS group only)		x	x	x	x
HbA1c	x			x	x
Fasting blood glucose	x			x	x

DOS=discharge order set, EMR=electronic medical record, PSS=Perceived Social Support scale, DES-SF=Diabetes empowerment scale-short form, In-Person clinic visits will be conducted at either CarPoint East or McCampbell Hall

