## H.2.b. Endpoints

**Primary:** Difference in the change in HbA1c from baseline to 24 weeks (+/-2 weeks) post-discharge (%, mmol/l)

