**Secondary:**

- Difference in the change in HbA1c from baseline to 12 weeks (+/-2 weeks) post-discharge (%, mmol/l)
- Difference in the change in HbA1c from baseline to 12 and 24 weeks (+/-2 weeks) post-discharge (%, mmol/l)
- Difference in the change in fasting plasma glucose (FPG) from baseline to 12 and 24 weeks in DOS vs ESC (mg/dl)
- Difference in the % of patients achieving HbA1C 7% in DOS vs ESC (12, 24 weeks)
- Difference in the % of patients achieving HbA1C 6.5% in DOS vs ESC (12, 24 weeks)
- Difference in the % of patients achieving individualized HbA1C target in DOS vs ESC (12, 24 weeks)
- Difference in the proportion of patients with accurate and complete discharge orders for basal insulin and related supplies. (%)
  - Assessed as complete dose, quantity dispensed, adequate refills (separate for basal and prandial insulin), and correct prescription for pen needles (presence, quantity, adequate refills), no jargon
- Difference in the proportion of patients with accurate and complete discharge orders for prandial insulin and related supplies. (%)
  - Assessed as complete dose, clear dosing instructions, quantity dispensed, adequate refills, and correct prescription for pen needles (presence, quantity, adequate refills), no jargon
- Difference in the proportion of patients with a discharge prescription for glucose monitoring supplies (%)
- Difference in adherence to glargine U300 (% taking >80% of doses) at 2, and 24 weeks
- Difference in the proportion of patients who remain on glargine U300 at 24 weeks (%)
- Difference in the mean dose of glargine U300 at 2 and 24 weeks (units)
- Difference in the frequency of glucose monitoring at 2 and 24 weeks (times per day)
- Difference in the proportion of patients who follow up with their primary care provider or endocrinologist within 2, 6 weeks of discharge (%)
- Difference in the incidence of documented symptomatic (BG <54 mg/dl) hypoglycemia (%)

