**H.2.c Primary Aim: To determine whether a Discharge order set with nursing support (DOS) is associated with lower HbA1c at 24 weeks post-program than enhanced standard care (ESC) alone.** We will test for a difference in 24 week change in HbA1c between the DOS and ESC groups using a linear mixed model for the longitudinal HbA1c measurements. Our model will contain a random subject-specific effect and fixed effects of time (baseline vs. 24 weeks), treatment, a treatment-by-time interaction, and baseline covariates related to change, which we expect to include age, whether or not patient is new to insulin, and dose of insulin based on our preliminary data. We will adjust for changes in prandial insulin dose by including dose as a time-varying covariate in our mixed models. The inclusion of covariates is not to account for differences in these factors across treatment groups (which we don't expect due to randomization) but to increase the precision of our treatment effect estimate. A Wald test of the treatment-by-time interaction will be used to test our primary hypothesis that DOS affects 24 weeks change in Hb1Ac.

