
➤ Set Meal Insulin Dose: appropriate for most patients using prandial insulin in addition to consistent carbohydrate diet
 
 
➤ Aspart U100 Flextouch pen and pen needles
 
➤ Glulisine U100 Solostar pen and pen needles
 
➤ Lispro U100 Kwikpen and pen needles
 
➤ Lispro U200 Kwikpen and pen needles
 
➤ Aspart U100 vial and syringes
 
➤ Lispro U100 vial and syringes
 
	
[Example Drop-down Menu:]
 
➤ Insulin Glulisine 100 Unit/ML Pen-injector      *** units SQ QAC.
 
 High dose correction
 
➤ Standard correction
 
 
 If your glucose is this	Add this much insulin to your mealtime dose	
 
 150-199	1	
 
 200-249	2	
 
 250-299	3	
 
 300-349	4	
 
 350-400	5	
 
 Over 400	6	
 
 
 Low dose correction
 
Dispense: 3 prefilled pens; Refills: 1
 
 Pen needle 31 G x 4 mm
 
For use with insulin 4 times daily
 
Dispense: 150; Refills: 1
	If your glucose is this	Add this much insulin to your mealtime dose	150-199	1	200-249	2	250-299	3	300-349	4	350-400	5	Over 400	6
If your glucose is this	Add this much insulin to your mealtime dose														
150-199	1														
200-249	2														
250-299	3														
300-349	4														
350-400	5														
Over 400	6														

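### The primary model adjusts for prandial insulin dose recorded after randomisation, so the tested coefficient need not be the total effect of the discharge order set

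*Combined protocol and SAP*

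**What the plan says.** Section H.2.c tests the primary hypothesis with a Wald test of the treatment-by-time interaction in a linear mixed model with a random subject effect. Three baseline covariates are expected: age, being new to insulin, and insulin dose. The section then adds: "We will adjust for changes in prandial insulin dose by including dose as a time-varying covariate in our mixed models". The next sentence says covariates are there "to increase the precision of our treatment effect estimate", and that arm differences in them are not expected because the trial is randomised.

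Other parts of the plan bear on this:

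- **Endpoint and purpose.** The primary endpoint in H.2.b is the arm difference in HbA1c change to 24 weeks, with no mention of equal prandial dose. H.1.a makes every analysis intention to treat. Section I says the aim is to evaluate the discharge programme as a whole.
- **Timing.** Table 9 lists randomisation and "Load DOS into EMR and inform discharge team" in the same visit 0 column.
- **Content of the order set.** It has prandial prescribing panels. Table 8 lists "Correction dosing from pick list of low, standard, or high doses", and the Appendix correction table is headed "Add this much insulin to your mealtime dose".
- **Secondary endpoint.** H.2.b includes "Difference in the proportion of patients with accurate and complete discharge orders for prandial insulin and related supplies".
- **Insulin dose at baseline.** H.2.c gives no time point for it. The total units named in D.2.e describe the discharge regimen: "The complexity of the discharge regimen will be assessed as number of injections per day, total units per day".

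**The concern.** Randomisation balances what is fixed before it. A prandial dose at discharge or during follow-up is not fixed before it, and the programme under test could alter that dose through its panels, its correction choices or earlier outpatient review. If it does, conditioning on dose removes that part of the programme's effect from the coefficient being tested. If dose also responds to poor glucose control, the coefficient may be neither the total effect nor the effect at equal dose.

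This is the trial's only powered test (H.2.a), and no primary model without the term is specified. Two definitions are also open. One is which prandial dose fills the baseline row (pre-admission, inpatient or discharge) and whether it is the dose prescribed or taken. The other is when the baseline insulin dose is recorded: if it is the discharge dose, that covariate too follows loading of the DOS.

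**Working it through.** **1. The plan's own figure.** H.2.a gives σ = 2.2, ρ = 0.25, R² = 0.5, Δ = 0.8, two-sided α = 0.05 and 80% power.

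- n per group = 4σ²(1−ρ)(1−R²)(1.960 + 0.842)²/Δ² = 4 × 4.84 × 0.75 × 0.5 × (2.802)²/0.64 = 89.04. The plan says 89.
- 89/0.8 = 111.25. The plan says 111.
- SE at 89 per group = √(4 × 4.84 × 0.75 × 0.5/89) = 0.286. Power = Φ(0.8/0.2856 − 1.96) = 80.0%.

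H.2.a defines R² for baseline covariates only, so the sample size does not depend on the time-varying dose.

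**2. What the tested coefficient becomes.**

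adjusted coefficient = total effect − (δ × θ)

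Here δ is the DOS-minus-control difference in prandial dose change and θ is the fitted HbA1c slope per unit of dose. The two sides agree only if δ = 0 or θ = 0.

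**3. Illustrative size.** The documents give neither δ nor θ, so both are assumed. Total effect −0.80. Simulation: random-intercept model fitted by REML, two visits, 89 per group, complete data, 2000 runs per case, one baseline covariate explaining half the variance of change. Assumed prandial dose: baseline mean 30 and SD 15, change noise SD 10.

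| δ (units/day) | θ = −0.02: formula / simulated | θ = −0.04: formula / simulated |
|---|---|---|
| 0 | −0.80 / −0.79 | −0.80 / −0.80 |
| +5 | −0.70 / −0.71 | −0.60 / −0.60 |
| +10 | −0.60 / −0.60 | −0.40 / −0.40 |
| −5 | −0.90 / −0.91 | −1.00 / −1.00 |

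Without the dose term, the estimate stayed between −0.79 and −0.81 in every case. With covariate-by-time terms in the model, power at δ = +10 was 54% or 28% with the dose term. Without it, power was 78–80% throughout. In the other direction, if the total effect were zero, an offset of 0.2 would give about 10.8% rejection at a nominal 5% (SE 0.286).

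**4. Dose that responds to glucose control.** A separate simulation, also with assumed inputs, let DOS raise dose by 10 units (total −0.80, direct −0.60) and let dose rise with poor control. The fitted slope turned positive (+0.010) and the adjusted estimate was −0.90, which is neither quantity.

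**5. Which dose fills the baseline row.** With the shift made at discharge and the same simulated patients (θ = −0.02 / −0.04):

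| Shift | Baseline row = pre-randomisation dose | Baseline row = discharge dose |
|---|---|---|
| +5 | −0.69 / −0.61 | −0.79 / −0.81 |
| +10 | −0.60 / −0.39 | −0.80 / −0.79 |

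**6. Precision gained.** The residual variance of change is 2 × 4.84 × 0.75 × 0.5 = 3.63. Dose noise adds θ² × 10², which is 0.04 or 0.16. With no shift, the dose term therefore cuts the SE only from 0.287 to 0.286, or from 0.292 to 0.286.

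**7. A related but separate power point.** In a complete two-visit model, a covariate main effect is the same at both visits and cancels from the change. R² = 0.5 is therefore realised only with covariate-by-time terms. With main effects alone, SE = √(4 × 4.84 × 0.75/89) = 0.404, power = Φ(0.8/0.4039 − 1.96) = 51%, and 80% power needs 178 evaluable per group.

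**The case against.** The case on the other side has five parts.

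- **The plan does voice a no-difference expectation.** It comes straight after the prandial sentence. True, but the ground given is randomisation, which cannot secure balance in a dose set later. The expectation is stated without support.
- **The route from DOS to prandial dose is thin.** The primary team sets the regimen in both arms (F.1.a, F.2.a). The Appendix leaves the meal dose blank for the prescriber, explicit titration is basal only (F.2.b), and Human Subjects A.1.c plans no prescriptive regimen. The prandial endpoint scores order quality, not dose size. All of this stands: influence on dose is possible, not shown.
- **Slopes, shifts and dose spread are assumed.** This stands. Step 4 shows that even the direction can reverse. The small precision gain also depends on the dose-change SD of 10. At SD 20 and slope −0.04, the residual variance without the term is 3.63 + 0.64 = 4.27, and the term would cut the SE from √(2 × 4.27/89) = 0.310 to 0.286. A larger gain would still not make the coefficient the total effect.
- **The 51% power figure is a different matter.** Agreed. It rests on reading H.2.c as main effects only, which the section does not say outright, and the main point does not need it.
- **Baseline insulin dose may well be pre-randomisation.** Table 6 requires current basal insulin at entry, so a basal dose is known by then. The timing still needs stating.

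**Conclusion.** The concern holds. As written, the only powered test conditions on a post-randomisation variable that the stated rationale does not cover. The coefficient equals the total DOS effect only if mean prandial dose change is the same in both arms or the fitted dose slope is zero. The distortion is conditional, and the documents fix neither its size nor its direction. Under the assumed inputs in step 3, an effect of −0.80 appears as anything from −0.40 to −1.00; with equal dose change it is unaffected. This should be settled before analysis, because it determines which question the primary test answers. The sample size formula is not in error.

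**What to change.** In H.2.c:

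1. Remove on-study prandial dose from the primary model.
2. Restrict covariates to those fixed before randomisation: age, new to insulin, and an insulin dose explicitly recorded before randomisation rather than taken from the discharge regimen. If pre-randomisation prandial use is wanted, treat it the same way.
3. Enter each covariate with a covariate-by-time term, so that it can reduce the variance of the change contrast.
4. Report any on-study dose-adjusted model only as a labelled exploratory analysis. State whether dose is prescribed or taken, at which visit, and which dose fills the baseline row.

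Keeping the term and declaring an equal-dose estimand would be coherent, but it would answer a different question from H.2.b and section I and would need assumptions about what drives dose.

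The cost is SAP wording. The 89 evaluable and 111 recruited per group do not depend on the removed term. The stated 80% power holds if the covariate-by-time terms are used and R² = 0.5 is right. D.2.e already collects concomitant medications, but it does not say that prandial doses are recorded, so the data form should be checked if one is wanted as a baseline covariate. The change also spares the primary analysis from imputing missing on-study prandial doses under H.1.a.

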#### H.2.d. Secondary Aims:

- Determine whether DOS is associated with lower HbA1c at 12 months compared to ESC.
- Determine whether the DOS in conjunction with nurse supported self-titration of basal insulin glargine U300 is associated with improved persistence with insulin therapy, adequate dose titration, and use of self-monitored blood glucose.
- Determine whether the DOS is associated with improved discharge instructions and processes of care for insulin-requiring patients. This will be measured in terms of clarity of instructions, adequacy and completeness of prescriptions for insulin and diabetes supplies, and follow-up plan.

Each of these secondary outcomes will be binary (e.g., adequate vs. inadequate dose titration). Missing values of the outcomes will be imputed using treatment group and baseline covariates. The difference in proportions between treatment groups will be computed for each data set and the results will be combined using Rubin's rules to obtain a final two-sample test of proportions.

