### **Secondary Aims:**

- Evaluate the efficacy of a diabetes focused DOS on reducing HbA1c at 12 weeks compared to ESC among hospitalized basal insulin requiring patients with uncontrolled diabetes.
- Evaluate the efficacy of a diabetes focused inpatient discharge order set (DOS) on change in fasting plasma glucose from baseline to 12 and 24 weeks.
- Evaluate the efficacy of a diabetes focused inpatient discharge order set (DOS) on % of subjects reaching HbA1c <7.0% or <6.5% at 12 and 24 weeks.
- Determine whether the DOS in conjunction with nurse supported self-titration of basal insulin glargine U300 is associated with improved persistence with insulin therapy, adequate dose titration, and use of self-monitored blood glucose.
- Determine whether the DOS is associated with improved discharge instructions and processes of care for insulin-requiring patients. This will be measured in terms of clarity of instructions, adequacy and completeness of prescriptions for insulin and diabetes supplies, and follow-up plan.

**Study Design:** In this 24 week randomized controlled trial, hospitalized insulin-requiring patients with type 2 diabetes and poor glycemic control (HbA1c >8.5%) will receive glargine U300 plus additional background therapy (non-insulin and prandial insulin therapies) with or without a diabetes focused discharge order set and follow-up communication to facilitate insulin titration and outpatient follow-up. Patients in the control group will receive traditional standard of care with the support of a patient care resource manager.

**Study Population:** Hospitalized patients with type 2 diabetes (HbA1c >8.5%) who are receiving basal insulin at least 10 unit per day and are able to provide informed consent will be approached. Patients must have access to some form of communication (phone, electronic patient messaging) post discharge and be willing to obtain HbA1c at follow-up. Patients will be identified through daily screening of the inpatient medical and surgical services throughout the institution.

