### H.2.a. Statistical Power and Sample Size

The sample size for our study was based on a comparison of change in HbA1c over three months adjusting for baseline covariates related to change in HbA1c: age, whether or not patient is new to insulin, and dose of insulin; the first two were selected based on our preliminary data and the latter was selected based on an expected relationship. The following expression, adapted from Oakes and Feldman, was used to calculate the number of individuals per group:

$$n/group = \frac{4\sigma^2(1-\rho)(1-R^2)(Z_{1-\alpha/2} + Z_{1-\beta})^2}{\Delta^2}$$

where  $\sigma$  is the standard deviation of HbA1c,  $\rho$  is the correlation between baseline and 24 week HbA1c levels,  $R^2$  is the proportion of variability in change in HbA1c explained by the baseline covariates,  $\Delta$  is the difference in change in HbA1c between treatment groups, and  $Z_{1-\alpha/2}$  and  $Z_{1-\beta}$  are standard normal quantiles calculated at the two-sided type-I error rate ( $\alpha$ ) and power (1- $\beta$ ). Using parameter values based on our preliminary data ( $\sigma = 2.2\%$ ,  $\rho = 0.25$ ,  $R^2 = 0.5$ ) and based on the effect observed by Wexler ( $\Delta = 0.8\%$ ), we will need 89 individuals per treatment group with 24 week follow-up to achieve 80% power at  $\alpha = 0.05$ . Since we expect 20% attrition, we will recruit 111 individuals per group into our study. The study is powered to detect a difference in the primary endpoint only. However, additional secondary endpoints of strong interest are pre-specified and included in the analysis.

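### H.2.d treats every outcome under its three aims as binary, which contradicts H.1.a and H.2.b for 12-week HbA1c, does not fit the dose and monitoring endpoints, and dates HbA1c at a time never measured

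*Combined protocol and SAP*

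**What the plan says.** H.2.d covers three aims: HbA1c; persistence with insulin, dose titration and self-monitoring; and discharge instructions and processes of care. One rule follows for all of them: "Each of these secondary outcomes will be binary (e.g., adequate vs. inadequate dose titration". Missing outcomes are imputed from treatment group and baseline covariates, a difference in proportions is computed in each imputed data set, and the results are pooled into a two-sample test of proportions.

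The HbA1c aim in that list reads: "Determine whether DOS is associated with lower HbA1c at 12 months compared to ESC". The synopsis words the same aim as: "Evaluate the efficacy of a diabetes focused DOS on reducing HbA1c at 12 weeks compared to ESC". Section D.1.b gives a range of 12 to 24 weeks.

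Two other sections bear on the method. H.1.a says: "Longitudinal outcomes (e.g., HbA1c) will be analyzed using mixed models utilizing all available measurements from individuals randomized". It confines outcome imputation to the binary case: "Missing binary outcomes (e.g., accurate and complete discharge orders, adherence) and missing covariate data will be imputed". H.2.b lists among its secondary endpoints "Difference in the change in HbA1c from baseline to 12 weeks (+/-2 weeks) post-discharge (%, mmol/l" and "Difference in the mean dose of glargine U300 at 2 and 24 weeks (units", together with monitoring frequency in times per day at 2 and 24 weeks.

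H.2.c specifies the primary mixed model, with time entered at two levels, baseline and 24 weeks.

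**The concern.** H.2.d is the section that sets out the analysis of the secondary aims, so an analyst will look there first. Followed literally, it sends 12-week HbA1c to a test of proportions, although the endpoint is a change on a continuous scale and no section gives a value at which to split it. It does the same to titration and monitoring, where the listed endpoints are a mean dose and a frequency. Its own example, adequate titration, has no definition anywhere, and H.2.b lists no such endpoint.

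At stake is pre-specification. H.2.a describes the secondary endpoints as pre-specified and of strong interest, and section J plans a manuscript on glycaemic control, titration and persistence. If the written rule cannot be run without inventing a threshold, the threshold or the departure from the rule would be settled later, possibly with data in view. The 12-month date adds an aim that the trial cannot measure.

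**Working it through.** **1. Outcome type.** The affected endpoints, compared across sections:

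| Endpoint | Scale in H.2.b | Rule in H.2.d | H.1.a |
|---|---|---|---|
| HbA1c, baseline to 12 weeks | change (%, mmol/l) | binary, imputed, proportions | mixed model; HbA1c named |
| Glargine U300 dose, 2 and 24 weeks | mean, units | binary, imputed, proportions | mixed model only if dose counts as a longitudinal outcome |
| Glucose monitoring, 2 and 24 weeks | times per day | binary, imputed, proportions | mixed model only if frequency counts as a longitudinal outcome |

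The HbA1c row is a direct conflict with both other sections, including on missing data, because H.1.a imputes outcomes only when they are binary. The other two rows are a mismatch with H.2.b. The remaining H.2.b proportions (HbA1c targets, complete discharge orders, supply prescriptions, adherence, remaining on U300, follow-up attendance) suit the H.2.d rule. Fasting plasma glucose change is continuous but belongs to none of the three H.2.d aims, so it is not in conflict.

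**2. Time point.** Table 9 schedules HbA1c at baseline, 12 and 24 weeks. D.2.f ends record queries at 24 weeks after enrolment, and section J puts the final visit at 6 months. With the window of plus or minus 2 weeks, the latest HbA1c falls at 24 + 2 = 26 weeks; 12 months is about 52 weeks. The synopsis and H.2.b both say 12 weeks, so that is the best-supported reading.

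**3. Week 12 in a model.** H.2.c has baseline and 24 weeks only, so its treatment-by-time term yields no 12-week contrast. H.1.a supplies a class of model without stating the one for week 12.

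**4. Design figures.** From H.2.a, σ = 2.2, ρ = 0.25, R² = 0.5, Δ = 0.8, two-sided α = 0.05 and power 80%:

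n per group = 4 × 2.2² × (1 − 0.25) × (1 − 0.5) × (1.960 + 0.842)² / 0.8² = 89.04 (stated: 89).

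With 20% attrition, 89 / 0.8 = 111.25 (stated: 111), and 2 × 111 = 222. No H.2.d outcome enters this calculation.

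**5. Illustration of power, not a finding.** Suppose the 24-week inputs held at week 12, with 89 per group and normally distributed change.

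- SD of change = 2.2 × √(2 × 0.75) = 2.694; after covariate adjustment, 2.694 × √0.5 = 1.905.
- Continuous and adjusted: 80% power.
- Continuous and unadjusted: 51%.
- Unadjusted proportions at the most favourable cut (44% against 56%): 35%.
- If the adjusted SD is used for the split instead (42% against 58%): about 60%.

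Losing covariate adjustment (80% to 51%) and dichotomising (51% to 35%) are separate losses, and the first is the larger. No section gives a cut.

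**The case against.** The strongest defence is that the plan read as a whole already resolves the HbA1c question. H.1.a uses HbA1c as its example for mixed models, its binary examples are discharge orders and adherence, and the H.2.d example is titration. All the binary examples belong to the second and third aims, so the author probably meant the rule for those two. This stands as an account of intent. It does not repair the text, because the rule follows a list that begins with HbA1c and covers each item in it.

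Several stronger conclusions are tempting, and the documents do not support them:

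- A reader might infer that two methods for 12-week HbA1c are equally open. They are not: the rest of the plan favours the mixed model.
- A reader might infer that week 12 is left without any model. H.2.c is the primary-aim model and has no duty to contain week 12, and the general rule in H.1.a reaches those data. What is missing is a specific statement.
- A reader might infer that dose and monitoring contradict H.1.a, or that H.2.d overrides it. H.1.a names only HbA1c, and no section sets an order of precedence. A binary titration outcome could also coexist with mean dose; the gap would then be an undefined outcome and no named test for the continuous ones.
- A reader might infer that the binary rule takes power from 80% to 35%. That comparison needs an invented cut and borrowed 24-week inputs, and most of the fall comes from dropping covariates.

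It is also fair to say that the plan makes no power claim for these endpoints: "The study is powered to detect a difference in the primary endpoint only".

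**Conclusion.** The point holds, within limits. As written, H.2.d prescribes an analysis that contradicts H.1.a and H.2.b for 12-week HbA1c, does not fit the H.2.b definitions of glargine dose and monitoring frequency, and names a 12-month HbA1c that will not exist. The contradictions rest on the text alone and need no numerical assumption. Reading 12 months as a slip for 12 weeks is an inference, well supported by the synopsis, H.2.b and the visit schedule.

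The reach is confined to secondary endpoints. The primary 24-week analysis and the sample sizes of 89, 111 and 222 are unchanged. The loss of power cannot be sized from the documents: they give no cut and no 12-week effect for HbA1c, and no standard deviation for dose or monitoring frequency. The correction should be made, since the section otherwise misdirects the analyst on the first secondary aim.

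**What to change.** 1. In H.2.d, change 12 months to 12 weeks, and bring the HbA1c aim in D.1.b into line with it.
2. Limit the binary, imputation and proportions rule in H.2.d to the endpoints that H.2.b defines as proportions.
3. State that 12-week HbA1c change is analysed by a separate mixed model with baseline and 12 weeks as its time levels, the treatment-by-time term giving the contrast. The primary model in H.2.c stays as it is.
4. State that glargine U300 dose and monitoring frequency are analysed as continuous outcomes by mixed or linear models.
5. If a binary outcome for adequate titration or monitoring use is to be kept, define it before outcome data are reviewed.

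The cost is SAP wording only: no added patients, visits or data, and no change to the primary analysis.
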